This study will employ a 2-arm randomised controlled trial, including 1 symptom monitoring intervention group and 1 non-monitoring control group. The main analysis will be a 2 by 2 mixed between/ within-subjects ANOVA. The between-subjects component will compare symptom differences between the symptom monitoring intervention group and the usual care control group. The within-subjects component will compare symptom changes between baseline and after 2-weeks of daily symptom monitoring, and between baseline and after an interval of 2 weeks without monitoring, in the control group. The interaction will establish whether symptom changes differ over time according to whether women are in the symptom monitoring or control group. It is expected that improvements in well-being will occur over time in the symptom monitoring group, in comparison to the control group e.g., positive reactions will increase from baseline, whereas negative reactions will decrease. Symptom reports will be collected using the DRK (Boivin & Takefman, 1995). The intervention group will record their symptoms at baseline and every day for 2-weeks (although only baseline to follow up changes will be subject to analysis), the control group will record their symptoms at baseline and after an interval of 2-weeks with no daily monitoring. The DRK has been used previously in randomised trials of women's reproductive health (e.g., Boivin & Takefman, 1995; Ockhuijsen et al., 2014) to establish the effects of symptom monitoring. This research will take place electronically, questionnaires will be presented to participants in the form of JISC Online Surveys and accompanying information will be attached to emails as Word documents. This study has been designed in this way in response to the ongoing 2020 COVID-19 pandemic. The study admin will be managed by [name] via a dedicated USW email address: [contact].

Research design figure:

All participants:

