Health awareness was assessed using the Health Consciousness subscale extracted from The Health Orientation Scale (HOS, $\alpha = 0.82$): This variable will be explored following evidence from the systematic review which suggested that symptom monitoring could increase health awareness. The items on the Health Consciousness subscale refer to an awareness of one's health. These items were designed to measure people's tendency to think about and to reflect about their health. People who endorse these items are those who think about that status of their physical health, and who in general are reflective about the nature of the health and wellness of their body (Snell et al., 1991). This measure was chosen for its simplicity, high reliability coefficient ($\alpha = 0.82$) and because it has been employed in a number of studies (Adejumo et al., 2017; Gordon et al., 2005; Sneyby & Snell, 2002). **See Appendix 10, page 5 to view a copy of the original HOS including the Health Consciousness subscale, see Appendix 1, page 5 to view how the Health Consciousness subscale will be presented on the baseline survey. See Appendix 3, page 2 to see how to Health Consciousness subscale will be presented on the follow-up survey. On the baseline and follow-up surveys the health consciousness subscale is presented together with the health anxiety subscale and titled “Thoughts about health questionnaire”.**

The Daily record keeping form (DRK): participants in both groups will complete the DRK at baseline and at follow-up. Only the intervention group will complete the DRK every day of the 2-week period.

An RCT conducted by Lancastle compared outcomes of implementing a positive reappraisal coping intervention, with a positive mood induction control, and a daily monitoring control as measured using the DRK (Lancastle, 2006). This study evaluated emotional reactions and physical symptoms among women experiencing 14-day IVF waiting periods. This research found significant improvements in physical symptoms within the daily monitoring group across the 2-week waiting period which suggests that 2 weeks is an adequate amount of time to generate observable effects of an intervention, using daily symptom monitoring.

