10. PARTICIPANTS

Discuss the number of participants required, from where the participants will be recruited, and the exclusion and inclusion criteria. Please include power calculations where applicable.

Participants will be recruited using a research poster which will be presented both on JISC's research participant finder service: www.callforparticipants.com and social media sites: Facebook, Instagram and Twitter. **See Appendix 7 to view the recruitment poster as presented on www.callforparticipants.com, and shared on social media sites.** All participants who meet eligibility criteria and research terms will be provided with a £20 Amazon voucher after completing the study to thank them for their time.

Participants will be randomised using online resource: www.randomizer.org. Randomizer is a free resource for researchers in need of a quick way to generate random numbers or assign participants to experimental conditions. This site can be used for a variety of purposes, including psychology experiments, medical trials, and survey research. Randomizer works by generating a series of random unique numbers, therefore to allocate participants into the intervention group 1 set of 39 random numbers were generated using values ranging from 1-78. These figures were chosen following insights from the power analysis (see below).

Random number generation will be used to allocate participants into groups. Participants will be assigned a number when they join the study by submitting the baseline survey- this number will reflect the order in which they joined the study i.e. the first person to join will be assigned as number 1, the second will be assigned as number 2. This number will determine whether they are in the control or intervention group by using random numbers generated by randomizer.com. Randomizer works by generating a series of random unique numbers, therefore, to allocate participants into the intervention group, 1 set of 39 random numbers will be generated using values ranging from 1-78. If the participant's assigned number matches one of the 39 random numbers generated, they will be allocated into the intervention group. If their number is not on the random number list, they will be allocated into the control group.

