Inclusion criteria: this study will involve adult females, who report at least 2 hot flushes per day, with self-reported peri- or post-menopausal status. Women taking menopause-specific treatments (e.g. HRT or anti-depressants) are included in this study provided they reach the criteria for hot flushes and are otherwise healthy.

Exclusion criteria: participants will be screened out of the survey if they answer no to the following questions, which will be presented before the information sheet, consent form and main survey: "Are you over the age of 18?", "Are you experiencing at least 2 hot flushes per day?", and "Are you experiencing either perimenopause or menopause?"

Additionally, care will be taken to identify and exclude outliers from analyses, especially when considering the data of those who say they have been diagnosed with chronic or severe conditions with symptoms overlapping with menopausal symptoms, including chronic fatigue syndrome, fibromyalgia, cancer, heart

**FACULTY OF LIFE SCIENCES AND EDUCATION
FACULTY ETHICS SUB GROUP APPLICATION FORM**

disease, thyroid disorders, depression and other mental illnesses. As the research team is not medically trained, we are not able to ascertain definitively if women do have any medical conditions. However, women will be informed in the information sheet that they should not participate if they have these conditions for the reason stated above, and those who report such conditions in the demographic and medical history will be statistically assessed with caution using univariate and multivariate analyses, and data from these individuals will be excluded where necessary. Participants who do not complete all study materials or comply fully with the experimental protocol will also be excluded from analyses. Participants who report demographic characteristics that have been related to poorer health will also be assessed as covariates. Differences in symptoms between groups according to employment status, living status and relationship status will be analysed to understand variances in health between these groups. This is because unemployed, or single, or individuals who live alone are more likely to report poorer health than others.

Power analysis:

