An a priori power analysis was conducted using G*Power 3 (Faul, Erdfelder, Lang, & Buchner, 2007) to test the difference between two independent group means (accounting for special, main effects, and interactions) using a two-tailed test, a medium effect size ($d = .40$) and an alpha of .05. Results suggested that a total sample of 52 participants with two equal sized groups of 26 was required to achieve a power of .80.

Medium effect sizes were estimated based on Cohen's (1962) conventional values because these values were derived from studies specific to psychological research (Aguinis, & Harden, 2009). Furthermore, medium effect estimates, rather than small estimates, were used for this research because this study is exploratory and small effects on symptom frequency might not be noticeable to participants. Small effects might imply that symptom monitoring as an intervention to help reduce menopausal symptoms may lack meaningful benefit.

Hoerger (2010) found evidence that at least 10% of participants will drop out of internet mediated research and such studies have high attrition rates. Furthermore, several studies have provided data on attrition rates of studies which employ a 2-week intervention period. Lancastle and Boivin's (2008) feasibility study aimed to establish whether a brief coping intervention (positive reappraisal coping intervention; PRCI) was acceptable and practical when evaluated in the context of a randomised trial. Of the 84 women who agreed to participate in the study 55 (65.5%) completed all measures, suggesting an attrition rate of 34.5%. Moreover, Lancastle's (2006) study also evaluated the PRCI alongside a positive mood inductive intervention, and a daily monitoring control group; this research reported a 31% attrition rate.

Therefore, taking into account average attrition rates from internet mediated research (10%), as well as studies which have utilised a 2-week intervention period (33%), it was decided that the proposed study will use a total sample of 78 participants with two equal groups of 39.

11. HAVE NATIONALLY APPROVED / REGULATORY BODY GUIDELINES BEEN FOLLOWED IN PREPARING THIS PROTOCOL?

(E.g. Association of the British Pharmaceutical Industry Guidelines (1983), Royal College of Physicians Guidelines, The Declaration of Helsinki, British Psychological Society guidelines, BERA, etc.). If so, please specify.

- Faculty of Life Sciences and Education Ethics Committee

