22. DATA ANALYSIS / STATISTICS

Please describe the arrangements for analysing your data (qualitative and quantitative). Where appropriate discuss what data/statistical analysis will be completed. Where used, please remember to discuss sample size and how the sample size was decided upon.

2 x 2 mixed between-within ANOVA:

The main analysis will include a 2x2 mixed between-within ANOVA to assess differences in symptoms among the symptom monitoring and control groups before and after the 2-week research period. The between-subjects component will encompass the differences in symptoms between the control and intervention groups; the within-subjects variable refers to differences in symptoms before and after the 2-week study period. It is expected that after 2 weeks of symptom monitoring the intervention group will exhibit a greater reduction in symptoms in comparison to the control group (i.e., a significant group x time interaction). As discussed, a power analysis was calculated to identify the minimum sample size needed to detect moderate effects, resulting in the decision to recruit 78 participants, with 39 participants being randomised into each group.

Regressions:

Multiple regressions will explore whether help-seeking intentions as continuous variables as predicted by symptom monitoring group (dummy coded), self-efficacy in patient-doctor communication, self-efficacy in shared decision making, health and symptom awareness, and self-efficacy in goal orientated behaviour, health anxiety, and menopausal symptom changes.

Logistic regressions will establish whether control or intervention group membership (as measured as a dichotomous “Invention/Control” variable) is predicted by health anxiety, variances in emotions and symptoms, help-seeking intentions, self-efficacy in patient-doctor communication, self-efficacy in shared decision making, health and symptom awareness, and self-efficacy in goal orientated behaviour.

Correlations:

FACULTY OF LIFE SCIENCES AND EDUCATION
FACULTY ETHICS SUB GROUP APPLICATION FORM

Correlations will also be computed to assess for associations between certain variables. For example, higher neuroticism X higher negative emotions.

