FACULTY ETHICS SUB GROUP APPLICATION FORM

I feel confident that I can understand the information enough to be able to make a choice					
I feel confident that I can ask questions without feeling dumb					
I feel confident that I can express my concerns about each choice					
I feel confident that I can ask for advice					
I feel confident that I can figure out the choice that best suits me					
I feel confident that I can handle unwanted pressure from others in making my choice					
I feel confident that I can let the clinic team know what's best for me					
I feel confident that I can delay my decision if I feel I need more time					

Self-efficacy scale:

20. Please read through the following statements and indicate how accurately they apply to you:

	1 = Not at all true	2 = Hardly true	3 = Moderately true	4 = Exactly true
I can always manage to solve difficult problems if I try hard enough				
If someone opposes me, I can find the means and ways to get what I want.				
It is easy for me to stick to my aims and accomplish my goals.				
I am confident that I could deal efficiently with unexpected events.				
Thanks to my resourcefulness, I know how to handle unforeseen situations.				
I can solve most problems if I invest the necessary effort.				
I can remain calm when facing difficulties because I can rely on my coping abilities.				

FACULTY OF LIFE SCIENCES AND EDUCATION
FACULTY ETHICS SUB GROUP APPLICATION FORM

When I am confronted with a problem, I can usually find several solutions.				
If I am in trouble, I can usually think of a solution.				
I can usually handle whatever comes my way.				

The Daily Record Keeping Form:

21. Please read through the following emotions and menopausal symptoms and indicate whether you have experienced them in the past 24 hours using this scale: **0= Not at all (you have not experienced this symptom or emotion at all in the past 24 hours)** , **1= Mild (you've experienced this symptom or emotion but it has not impacted your daily activities or made you feel any different than usual)** , **2= Moderate (you've experienced this symptom or emotion and it has impacted your daily activities to some degree or made you feel somewhat different than usual)** , **3= Severe (you've experienced this symptom or emotion and it has heavily impacted your daily activities or made you feel extremely different than usual)**.

	0= Not at all	1= Mild	2= Moderate	3= Severe
Nervous				
Positive				
Relieved				
Sad				
Hopeful				

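### The main test is a change-score comparison; ANCOVA on the baseline DRK score already collected would generally be more precise, by an amount the documents do not let us fix

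*Combined protocol and SAP*

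**What the plan says.** Section 8 (Statement of study design): "The main analysis will be a 2 by 2 mixed between/ within-subjects ANOVA". The same section says that, although the intervention arm fills in the DRK daily, only the change from baseline to follow-up is analysed. Section 22 (Data analysis / statistics) gives the expected finding: the "intervention group will exhibit a greater reduction in symptoms in comparison to the control group (i.e., a significant group x time interaction").

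The baseline score is available in both arms. Section 9, under the DRK, says that "participants in both groups will complete the DRK at baseline and at follow-up". It is also measured before allocation. Section 10: "Participants will be assigned a number when they join the study by submitting the baseline survey", and that number decides the group.

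The only covariates mentioned are demographic. Section 10: "Participants who report demographic characteristics that have been related to poorer health will also be assessed as covariates". No model is named for them. Section 7 likewise raises only living, relationship and employment status as covariates. The regressions in Section 22 have help-seeking or group membership as the outcome, so none of them estimates the effect on symptoms given baseline.

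On size, the power analysis in Section 10 says: "Results suggested that a total sample of 52 participants with two equal sized groups of 26 was required to achieve a power of .80". Recruitment is set at 78 to allow for attrition. The analysed set is restricted: "Participants who do not complete all study materials or comply fully with the experimental protocol will also be excluded from analyses".

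**The concern.** The interaction in a two-arm, two-time ANOVA compares mean change between arms. Subtracting baseline amounts to assuming that each extra point at baseline carries over in full to follow-up. Where the true slope is below 1, the subtraction over-corrects and adds noise. ANCOVA estimates the slope from the data and, in large samples, is never less precise.

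This matters because the trial expects to analyse only about 52 women, and the covariate costs nothing to collect. The size of the gain depends on r, and the documents point both ways. The DRK asks women to "indicate whether you have experienced them in the past 24 hours using this scale", so each score rests on a single day, which pulls r down. Slow-moving items such as weight gain, hair loss and brittle nails pull it up.

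**Working it through.** **Inputs.** From Section 10: stated effect d = 0.40, two-sided alpha 0.05, power 0.80, 52 analysed (26 per arm), 78 recruited. Not in the documents: r and the SDs. I assume r from 0.3 to 0.9 and, at first, SD = 1 at both times.

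**The plan's own figures.**
- Attrition: 52/(1 − 0.33) = 77.6, so 78. This reproduces.
- The 52 does not follow from d = 0.40. A two-sample t-test needs 100 per arm for 80% power, and 26 per arm gives 29%. A difference of 0.80 SD does need 26 per arm (power 81%). That is a separate point, but it is why both effect sizes appear below; 0.80 is an inference, not a figure in the plan.

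**Step 1: identity.** On one simulated data set with 26 per arm, the interaction F was 3.0375 and the squared change-score t was 3.0375.

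**Step 2: variances.**
- Change score: 2(1 − r).
- ANCOVA residual: 1 − r².
- Ratio, ANCOVA to change score: (1 − r²)/[2(1 − r)] = (1 + r)/2.
- Expected cost of estimating one slope at 26 per arm: factor 1 + 1/(52 − 4) = 1 + 1/48 = 1.021.

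At r = 0.5, for example, the ratio is 0.75, and 0.75 × 1.021 = 0.766, a cut of about 23%.

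| r | Change-score variance | ANCOVA variance | Large-sample cut | Cut at 26 per arm |
|---|---|---|---|---|
| 0.3 | 1.40 | 0.91 | 35% | 34% |
| 0.5 | 1.00 | 0.75 | 25% | 23% |
| 0.7 | 0.60 | 0.51 | 15% | 13% |
| 0.8 | 0.40 | 0.36 | 10% | 8% |
| 0.9 | 0.20 | 0.19 | 5% | 3% |

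A simulation of 40,000 trials agreed with the last column, with type I error about 0.05 for both methods. Below r = 0.5 the change-score variance exceeds 1, so the planned test is noisier than comparing follow-up scores alone. With equal SDs, ANCOVA falls behind only when (1 + r)/2 × 1.021 > 1, that is, above about r = 0.96.

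**Step 3: power at 26 per arm** (noncentral t, 50 v 49 df, slope cost included).

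| r | 0.40 SD: change → ANCOVA | 0.80 SD: change → ANCOVA |
|---|---|---|
| 0.3 | 22% → 31% | 67% → 84% |
| 0.5 | 29% → 37% | 81% → 90% |
| 0.7 | 45% → 50% | 95% → 98% |
| 0.8 | 61% → 65% | 99% → just under 100% |
| 0.9 | 88% → 89% | no practical gain |

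Analysed per arm for 80% power at 0.40 SD: 139, 100 and 60 with the change score, against 91, 76 and 52 with ANCOVA, at r = 0.3, 0.5 and 0.7.

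**Step 4: unequal SDs.** With k the follow-up/baseline SD ratio, the large-sample cut is 1 − k²(1 − r²)/(1 + k² − 2rk).

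| k | r = 0.3 | 0.5 | 0.7 | 0.8 | 0.9 |
|---|---|---|---|---|---|
| 0.8 | 50% | 43% | 37% | 36% | 39% |
| 1.25 | 22% | 11% | 2% | 0% | 5% |
| 1.25, with the 1/48 cost | 20% | 9% | 0% | −2% | 3% |

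**Step 5: what a chance imbalance does.** The standard error of the baseline difference is √(2/26) = 0.28 SD. An imbalance of that size moves the change-score estimate by (1 − r) × 0.28 = 0.19, 0.14 or 0.08 SD at r = 0.3, 0.5 or 0.7. This is already part of the variance in Step 2 and is not an additional harm; it shows where the lost precision comes from.

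**The case against.** The planned ANOVA is not an error. It is valid under randomisation and answers the question as posed, whether change differs by group. It also uses baseline, with slope 1, so the accurate description is that it does not condition on baseline. All of that stands.

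The gain is unknown and could be small. With a follow-up SD 1.25 times the baseline SD and r = 0.7 to 0.8, ANCOVA at 26 per arm is level or about 2% worse. That stands too, but 2% is about the most that can be lost, against a possible gain of a third with equal SDs, or about half when k = 0.8 and r is low.

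At the stated 0.40 SD, power is no better than about 50% under either method up to r = 0.7, so the change does not alter the trial's prospects. True: the sample size is a separate problem that this does not solve.

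The exclusion of non-compliers after randomisation, with 14 daily forms demanded of one arm only, makes equal randomised groups of 26 an idealisation. This stands, and it applies to both methods. An imbalance in that set need not be chance, and neither analysis is guaranteed unbiased there.

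Lastly, naming the DRK scores can be called a separate matter. Section 9 does list emotional facets, but it does not say how items are scored into them, and no ANCOVA can be specified until the score is.

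**Conclusion.** The concern holds. The main test is the change-score t-test, baseline DRK is a true pre-randomisation covariate, and no section plans to condition on it. The loss is of precision, not validity. With equal SDs and 26 analysed per arm it is about 34% to 3% of the variance over r = 0.3 to 0.9. Over SD ratios of 0.8 to 1.25 it runs from about half to nothing, or to a penalty of about 2%. These figures rest on assumed r and SDs, equal arms, and an analysed set that behaves as randomised. The amendment should be made because it costs almost nothing, but the trial does not stand or fall on it.

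**What to change.** 1. Name the DRK score or scores to be analysed and how the items form them. No total is defined, and Section 8 expects positive and negative reactions to move in opposite directions, so these need separate scores.
2. For each, make the main analysis ANCOVA: follow-up score = group + baseline value of the same score. Report the adjusted mean difference with its 95% CI. Keep the 2x2 ANOVA as supporting.
3. Use the same form for the other outcomes measured at both times.
4. Do not use a model that constrains the baseline means to be equal unless all randomised women are analysed.
5. Add demographic covariates only if named, with their coding, in advance.

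The change should be written in before outcome data are seen, so that the choice of analysis cannot depend on results.

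**Cost:** wording only, with no new data. It uses one residual degree of freedom and about 2% in variance at 26 per arm (1/48). Three demographic terms on top, at one degree of freedom each, bring the expected cost to 4/45, about 9%, if they explain nothing. The living, relationship and occupation items in Appendix 1 have many response options, so uncollapsed coding would cost more.
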